- k The Week 16 MRI may be collected up to 10 days **prior** to Week 16 (Visit 8). It is strongly recommended that the Week 16 MRI be collected prior to the Week 16 (Visit 8) dosing. If patients discontinue study participation prior to Week 16, MRI of the SIJ should be collected at ETV. For ETV, MRI requirements are dependent on the timing of study discontinuation. If discontinuation is:
  - at or before Visit 5, no MRI is required at ETV.
  - after Visit 5 up to and including Visit 8 (Week 16), MRI is required at ETV.
  - after Visit 8, MRI is required only if ETV occurs on or after Visit 12.
- l An x-ray of the SIJ will be performed during the Screening Period (Period 1) unless an x-ray taken within 6 months prior to screening is available and of good quality. All x-rays require central reading **ONLY**, regardless of date taken. Central reading will define eligibility using the mNY criteria to exclude patients with definite sacroiliitis on x-ray.
- m Cervical and lumbar spine only; serves as baseline for potential later assessments of structural changes. X-ray does not need to be repeated if one is available that was taken  $\leq 3$  months prior to screening (Visit 1; refer to Sections 5.2 and 5.3) and has passed quality assessment by central reading vendor.
- n A Self-Harm Follow-Up Form must be completed for each discrete event identified on the Self-Harm Supplement Form.
- o HLA-B27 test will be performed centrally.
- p Approval from the Lilly clinical research physician or clinical research scientist must be obtained before a CRP retest is permitted. If the CRP lab is retested, the most recent value will be used for randomization.

- q TB test(s) include PPD, QuantiFERON®-TB Gold, and T-SPOT®. See Section 8.4.6 for detailed description of TB testing. In countries where the QuantiFERON-TB Gold test or T-SPOT is available, either test may be used instead of the PPD TB test. The QuantiFERON-TB Gold test may be performed locally or centrally; the T-SPOT must be performed locally. PPD tests must be read 2 to 3 days after Visit 1.
- r For female patients  $\geq 40$  and  $< 60$  years of age who have had a cessation of menses for at least 12 months, an FSH test will be performed to confirm nonchildbearing potential (FSH  $\geq 40$  mIU/mL). FSH test will be performed centrally.
- s All patients will be tested for HBV at screening. Patients who are HBcAb+ at screening, regardless of HBsAb status, will have a serum HBV DNA obtained by the central laboratory. Patients who are found to be HBV DNA positive (detectable) at screening will be excluded from the trial. Patients who are HBV DNA negative (undetectable) may be enrolled into the study with required HBV DNA monitoring every 3 months during treatment and 12 weeks after the last dose of ixekizumab. If the result of the HBV DNA testing is positive, the patient must be discontinued from the study treatment and should receive appropriate follow-up medical care (refer to Section 8.4.10.2 for further information regarding the timing of discontinuation).
- t Only for females of childbearing potential. Serum pregnancy test will be done at Visit 1 only and will be performed centrally. Patients determined to be pregnant will be discontinued from treatment and will no longer be administered investigational product (see Section 7.1). Patients will undergo urine pregnancy testing at the clinic during designated scheduled visits through Week 52. Additional urine pregnancy testing can be performed at the investigator's discretion. If required per local regulations, urine testing for pregnancy may occur at intervals as required during the study treatment period and/or follow-up period.
- u For the fasting lipid profile patients are to not eat or drink anything except water for 12 hours prior to test.
- v Where collection is allowed by local regulations.
- w Only serum and plasma are collected at this visit.
- x Immunogenicity samples may also be analyzed for ixekizumab serum concentration to facilitate in the interpretation of immunogenicity data. An additional blood sample will be collected, when possible, for any patient who experiences a potential systemic allergic/hypersensitivity reaction during the study as judged by the investigator.
- y PK samples are to be collected before investigational product injection.
- z The Week 52 MRI may be collected up to 10 days **prior** to Week 52 (Visit 15).
- aa Patients who have taken at least 1 study dose and who discontinue study treatment prior to Week 16 or study participation (regardless of timing) are to complete an ETV and enter into post-study follow-up for at least 12 weeks after the ETV date or the last regularly scheduled visit. Patients whose ETV or last regularly scheduled visit is longer than 12 weeks after their last investigational study medication dose are not required to enter into the Post-Study Follow-Up Period (Period 3). Patients who complete the study through Week 52 and who are not entering into Study RHBX are to enter into the Post-Study Follow-Up Period (Period 3). Visits 801 and 802 are scheduled at 4 and 12 weeks (respectively) after the date of the last patient visit. Visit 803 will occur if a patient's neutrophil counts have not returned to the criteria defined in Section 8.4.10.1.
- bb Weight is only captured on eCRF at V2, V8, V10, V15, and/or ETV. Body weight collected at other visits is used only for calculation of creatinine clearance.
- cc If not completed at Visit 2, the sample should be collected as soon as possible at the next scheduled visit.
- dd If MRI is conducted on the same day as study visit, ensure that any scales/questionnaires are completed prior to administering any premedication to facilitate patient undergoing an MRI (for example, morphine or equivalent for significant pain as judged by the investigator or a benzodiazepine for claustrophobia).
- ee For all patients, screening MRI of the SIJ must be completed  $\leq 30$  days prior to randomization (refer to Sections 5.3 and 5.4).

---

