**Safety Population:** Safety analyses for Period 2 will be conducted on the Safety Population, defined as all randomized patients who received at least 1 dose of study treatment. For patients who were deemed as inadequate responders by their investigators and were treated with biologic rescue of ixekizumab 80 mg Q2W, only data up to the time of initiation of biologic rescue of ixekizumab 80 mg Q2W will be included in the Period 2 analyses. Patients will be analyzed according to the treatment to which they were assigned at Week 0.

**Inadequate Responder (IR) Population:** Selected safety and efficacy summaries will be provided for the IR Population, defined as inadequate responders (identified by investigators based on clinical judgment) who had initiated biologic rescue of ixekizumab 80 mg Q2W.

**Follow-Up Population:** Safety analyses for Period 3 will be conducted on the Follow-Up Population, defined as all randomized patients who received at least 1 dose of study treatment and have entered the Period 3. Patients will be analyzed according to the treatment they received before entering the Follow-up Period.

[Table RHBX.6.1](#) summarizes the major analysis purposes intended for each analysis population.

[Table RHBX.6.2](#) describes the treatment groups and the comparisons for each study period and analysis population.

Table RHBX.6.1. Major Analysis Purposes Intended for Each Analysis Population

	Intent-to-Treat (ITT) Population	Per-Protocol Set (PPS)	Inadequate Responder (IR) Population	Safety Population	Follow-Up Population
Disposition	x		x		x
Baseline Characteristics a	x		x		
Treatment Compliance			x	x	
Concomitant Medication	x		x b		
Protocol Deviation	x		x b		
Exposure			x b	x	
Efficacy and Health Outcomes Analyses	x	For ASAS40	Selected efficacy b		
Safety Analyses			Categorical safety b	x	x
Subgroup Analyses on Efficacy	x				
Subgroup Analyses on Safety Outcome				x	

Abbreviation: ASAS40 = Assessment of Spondyloarthritis International Society 40.

a Including patient demographics and other baseline characteristics, historical illness, preexisting conditions, prespecified medical history, previous therapy.

b These summaries will focus on the time period during biologic rescue of ixekizumab 80 mg every 2 weeks (Q2W).

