#### **6.1.2.2. Inadequate Responder Population**

The treatment period for biologic rescue of ixekizumab 80 mg Q2W starts at the time of first injection of biologic rescue of ixekizumab 80 mg Q2W on or after Week 16 (Visit 8) and ends at the date of study treatment discontinuation for patients who did not initiate other biologic therapy, or at the start of other biologic treatment for patients who initiated other biologic therapy.

The treatment period for other biologic rescue (excluding ixekizumab 80 mg Q2W) starts at the time of first injection of other biologic rescue and ends on the date of Week 52 (Visit 15) or the ETV/last regularly scheduled visit.

For efficacy analyses on the IR Population, baseline is defined as the last nonmissing assessment recorded on or prior to the date of first study drug injection at Week 0 (Visit 2). For safety analyses, baseline and baseline period are defined as the last nonmissing assessment prior to the first injection of biologic rescue of ixekizumab 80 mg Q2W. For treatment-emergent adverse events (TEAEs) during biologic rescue with ixekizumab 80 mg Q2W, baseline is the event ongoing just prior to the first injection of biologic rescue of ixekizumab 80 mg Q2W; for TEAEs during other biologic rescue, baseline is the event ongoing just prior to the first injection of other biologic rescue (excluding ixekizumab 80 mg Q2W).

For IR Population, efficacy measures after initiation of biologic rescue of ixekizumab 80 mg Q2W will be summarized by originally assigned treatment group without inferential statistics. If sufficient patients took other biologic rescue after taking biologic rescue of ixekizumab 80 mg Q2W, additional efficacy summary may be provided.

The categorical safety measures will be summarized with incidence rates only.

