The number and percentage of patients with treatment-emergent or follow-up emergent high or low vital sign and weight at any time for Periods 2 and 3, respectively, will be summarized. The comparisons between and among treatment groups will be conducted using Fisher's exact test for the Safety Population for Period 2.

- [Table RHBX.6.9](#) defines the high and low baseline values as well as the limits that are specified as treatment-emergent and follow-up emergent. Note that weight does not have an abnormal baseline; therefore, the treatment-emergent and follow-up emergent values are determined by change from baseline.
- All postbaseline scheduled, unscheduled, and repeated measurements will be included.
- To assess increases, change from the maximum value during the baseline period or baseline to the maximum value during each study period will be used.
- To assess decreases, change from the minimum value during the baseline period or baseline to the minimum value during each study period will be used.
- For treatment-emergent high and low:
  - A treatment-emergent **high** result is defined as a change from a value less than or equal to the high limit at baseline to a value greater than the high limit at any time that meets the specified change criteria during the treatment period.
  - A treatment-emergent **low** result is defined as a change from a value greater than or equal to the low limit at baseline to a value less than the low limit at any time that meets the specified change criteria during the treatment period.
- For follow-up emergent high and low:
  - A follow-up emergent **high** result is defined as a change from a value less than or equal to the high limit at baseline to a value greater than the high limit at any time that meets the specified change criteria during the follow-up period.
  - A follow-up emergent **low** result is defined as a change from a value greater than or equal to the low limit at baseline to a value less than the low limit at any time that meets the specified change criteria during the follow-up period.

**Table RHBX.6.9. Categorical Criteria for Abnormal Treatment-Emergent Blood Pressures and Pulse Measurement, and Categorical Criteria for Weight Changes for Adults**

Parameter	Low	High
Systolic BP (mm Hg) a (supine or sitting – forearm at heart level)	≤90 and decrease from baseline ≥20	≥140 and increase from baseline ≥20

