Diastolic BP (mm Hg) a (supine or sitting – forearm at heart level)	≤50 and decrease from baseline ≥10	≥90 and increase from baseline ≥10
Pulse (bpm) a (supine or sitting)	<50 and decrease from baseline ≥15	>100 and increase from baseline ≥15
Weight (kg)	(Loss) decrease from baseline ≥7%	(Gain) increase from baseline ≥7%

Abbreviations: BP = blood pressure; bpm = beats per minute; kg = kilogram; mm Hg = millimeters of mercury.

a Baseline abnormal values are defined by the value presented.

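### Weight enters the eCRF at only three of eleven scheduled post-baseline visits in Period 2 and at none in Period 3, which does not match the any-time weight-change analysis in SAP 6.13.5

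*Protocol*

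**What the plan says.** The Schedule of Activities (Protocol Appendix 2) has weight measured at V1, V2, V5 to V15, the ETV and V801 to V803, that is, at every visit except V3 and V4. Footnote bb then limits what is recorded: "Weight is only captured on eCRF at V2, V8, V10, V15, and/or ETV". It adds: "Body weight collected at other visits is used only for calculation of creatinine clearance".

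SAP 6.13.5 counts patients with "treatment-emergent or follow-up emergent high or low vital sign and weight at any time for Periods 2 and 3", and for this count it says: "All postbaseline scheduled, unscheduled, and repeated measurements will be included". Table RHBX.6.9 sets the weight criterion at a loss or gain of at least 7% from baseline. The same section plans box plots of physical characteristics, which include weight, at each visit, and says that categorical safety data will be summarised for the Inadequate Responder (IR) Population.

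Two further rules matter for rescued patients. For the Safety Population, SAP 6.1.1 says that "only data up to the time of initiation of biologic rescue of ixekizumab 80 mg Q2W will be included in the Period 2 analyses". For the IR Population, SAP 6.1.2.2 says: "For safety analyses, baseline and baseline period are defined as the last nonmissing assessment prior to the first injection of biologic rescue".

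Neither document reconciles footnote bb with these analyses.

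**The concern.** An any-time incidence is only as complete as the measurements behind it. Here the SAP text assumes every post-baseline weight, while the protocol keeps about a quarter of the scheduled Period 2 weights and none from follow-up. Three consequences follow if the text stands:

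- Period 2 incidence can miss a 7% change that comes and goes between captured visits, or that arises after the last captured weight and before rescue.
- Follow-up-emergent weight has a baseline (V15 or ETV) but no post-baseline eCRF value.
- For rescue at a visit without a captured weight, the last value before the first rescue injection is an old one. Change between that value and rescue then drops out of the randomised arm and appears under rescue ixekizumab. That includes change on placebo, for patients rescued from placebo.

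The stake is what the study report says about weight. No efficacy result is involved.

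**Working it through.** The documents give no figure for the weight analyses, so there is nothing to reproduce. Steps 1 to 3 are counts from the schedule. Step 4 rests on assumptions.

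**1. Period 2 capture.** Scheduled post-baseline weights are V5 to V15, at Weeks 4, 8, 12, 16, 20, 24, 28, 32, 36, 44 and 52, so 11. Captured are V8, V10 and V15 (Weeks 16, 24 and 52), so 3. 3/11 = 27%. The intervals between captured weights are 16, 8 and 28 weeks.

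**2. Period 3 capture.** V801 and V802 (required) and V803 (as needed) all have weight measured. None is on the footnote bb list: 0 of 3.

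**3. Age of the rescue baseline.** Rescue is allowed from Week 16 to Week 44 (Protocol 6.1). Lag = rescue week minus week of the last captured weight. Share = lag / (52 minus week of that weight), the part of the baseline-to-Week 52 interval that precedes rescue.

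| Rescue visit | Last captured weight | Lag (weeks) | Share before rescue |
|---|---|---|---|
| V8 (W16) | W16 | 0 | 0% |
| V9 (W20) | W16 | 4 | 4/36 = 11% |
| V10 (W24) | W24 | 0 | 0% |
| V11 (W28) | W24 | 4 | 4/28 = 14% |
| V12 (W32) | W24 | 8 | 8/28 = 29% |
| V13 (W36) | W24 | 12 | 12/28 = 43% |
| V14 (W44) | W24 | 20 | 20/28 = 71% |

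The zero lags assume that weight is taken before the injection. Rescue at V10 or later leaves one scheduled captured weight afterwards (V15).

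**4. Illustrative size.** The documents give no weight variability. Assume a true percent change with SD 3-6% over 52 weeks, plus independent measurement noise of SD 0.5-1% at each visit, baseline included. Two models were simulated, with 400,000 patients per scenario: a random walk (variance growing with time) and linear drift (a constant slope per patient). The share missed is 1 minus (share with a gain of at least 7% at Weeks 16, 24 or 52) / (share with such a gain at any of the 11 visits).

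- Random walk: 22-36% missed. At SD 5% and noise 0.5%, 9.3% are detected against 12.2%; 1 - 9.3/12.2 = 24%.
- Linear drift: 0-13% missed. At the same SD and noise, 8.3% against 8.4%.
- With noise raised to 1-2%, slope SD 3-5%, and losses counted as well as gains, linear drift misses 7-44%. The top figure (11.4% against 20.4%, at SD 3% and noise 2%) mostly reflects noise crossing the threshold: with a slope SD of 3%, a true 52-week change of 7% is 7/3 = 2.3 SDs, about 2% of patients in both directions together.

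For rescue, at SD 5% and noise 0.5%, the share flagged with a change of at least 7% in either direction after rescue, from the last captured weight against from the rescue-visit weight, is:

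- Random walk: rescue at W20, 9.7% v 7.9%; W28, 6.1% v 4.4%; W44, 6.1% v 0.1%.
- Linear drift: rescue at W44, 1.2% v 0.0%.

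For W44 rescue under the random walk, gains of at least 7% detected before rescue are 2.5% with captured weights and 9.6% with all weights.

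**The case against.** The strongest case against is that footnote bb is a deliberate rule applied equally to all arms, that weight is not an adverse event of special interest, and that any time can mean any recorded value. Several parts of this stand.

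- A reader might infer that weight gain on randomised treatment is broadly under-counted. The documents do not support that. A change that persists is picked up at the next captured visit unless rescue intervenes, and the linear-drift result shows how little may be lost.
- A reader might take the 6.1% v 0.1% pair as typical of rescued patients. It is the worst case: Week 44 is the last permitted rescue visit, Protocol 6.8.2 discourages therapy changes in the 8 weeks before Week 52, and rescue at Weeks 16 and 24 has a same-visit weight. How many patients are rescued late is not stated.
- A reader might infer that rescue-emergent weight is a firm planned output. SAP 6.13 lists treatment-emergent vitals for the IR Population without naming weight, and Protocol 8.4.2 defines vital signs as blood pressure, pulse and temperature. Inclusion is implied by SAP 6.13.5 and Table RHBX.6.9, which handle weight alongside vital signs. These IR summaries carry no between-group comparison.
- A reader might infer that no Period 3 weights exist. Footnote bb speaks of the eCRF. Creatinine clearance is on the chemistry panel, which goes to the central laboratory, and its data are transferred to the sponsor (Protocol 8.4.3, 10.2.1, Appendix 3). Whether weights come with that transfer cannot be seen.
- The SAP revision history records that Period 3 analyses were removed from 6.13.5. That is no error in itself, but it suggests that the remaining follow-up-emergent wording may be unintended.

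None of this removes the mismatch. The SAP asks for all post-baseline weights, and the protocol limits the use of most of them to one laboratory calculation.

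**Conclusion.** The point holds as a mismatch between data capture and planned analysis, and it is minor. Without any assumption, the current text leaves 3 of 11 scheduled weights for the Period 2 analysis and no eCRF weight for the Period 3 one. Also without assumption, the last captured weight is 4 weeks old at rescue in Weeks 20 and 28, 8 in Week 32, 12 in Week 36 and 20 in Week 44. That these lags distort a reported rescue summary is conditional on weight being included in it, and the effect falls mainly on late rescue.

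The size of the Period 2 under-count is uncertain, because it depends on how weight moves: 22-36% of gains missed under a random walk, 0-13% under linear drift, both with assumed SD 3-6% and noise 0.5-1%. It should not be quoted as one number. Efficacy, power and alpha are untouched.

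**What to change.** Change footnote bb so that the weights already measured at V5 to V15, the ETV and V801 to V803 are captured, either through an eCRF field or by transfer of the weights used for creatinine clearance. Use them in SAP 6.13.5, and name the pre-injection weight at the rescue visit as the baseline for any rescue-emergent weight summary. Period 2 would then have 11 scheduled post-baseline weights and a rescue lag of 0 weeks at every rescue visit. Period 3 would have two required weights and one as-needed weight.

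State in SAP 6.13 whether weight belongs in the IR Population summaries.

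If the weights cannot be recovered, or if Period 3 weight analysis is not intended, delete follow-up-emergent weight from 6.13.5 and do not report rescue-emergent weight change where the last captured weight is not from the rescue visit.

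The cost is a little more data entry or one data transfer, plus a few lines of SAP text. No procedure is added for patients.

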## Appendix 3. Clinical Laboratory Tests

---

### Clinical Laboratory Tests

| Hematologya:                                     | Serum Chemistrya:                                      |
|--|--|
| Hemoglobin   | Sodium   |
| Hematocrit   | Potassium  |
| Erythrocyte count (RBC)  | Bicarbonate  |
| Mean cell volume (MCV)   | Chloride   |
| Mean cell hemoglobin concentration (MCHC)                          | Phosphorus   |
| Leukocytes (WBC)   | Total bilirubin  |
| Platelets  | Direct bilirubin   |
| Absolute counts of:   | Alkaline phosphatase   |
| Neutrophils, segmented   | Alanine aminotransferase (ALT/SGPT)                                      |
| Neutrophils, juvenile (bands)                                      | Aspartate aminotransferase (AST/SGOT)                                    |
| Lymphocytes  | Blood urea nitrogen (BUN)  |
| Monocytes  | Uric acid  |
| Eosinophils  | Creatinine   |
| Basophils  | Calcium  |
| Urinalysis (dipstick)a:                          | Glucose  |
| Color  | Albumin  |
| Specific gravity   | Cholesterol (total)  |
| pH   | Total protein  |
| Protein  | Calculated creatinine clearance  |
| Glucose  | Creatine phosphokinase (CPK)   |
| Ketones  | Triglycerides  |
| Bilirubin  | Gamma-glutamyl transferase (GGT)   |
| Urobilinogen   |  |
| Blood  | Lipid Panelc   |
| Nitrite  | Low density lipoprotein (LDL)  |
| Urine creatinine   | High density lipoprotein (HDL)   |
| Leukocyte esterase   | Very low density lipoprotein (VLDL)                                      |
| Other Tests:  |  |
| Human immunodeficiency virus antibody (HIV) f           | Pregnancy test (serum) d                                      |
| Hepatitis B surface antigen (HBsAg) f                   | Follicle-stimulating hormone (FSH) e                          |
| Anti-hepatitis B surface antibody (HBsAb) f             | Thyroid-stimulating hormone (TSH) and free T4                            |
| Anti-hepatitis B core antibody (HBcAb) f                | Ixekizumab serum concentration (pharmacokinetic)                         |
| Anti-hepatitis C antibody f,h                           | Partial thromboplastin time (PTT)  |
| HBV DNA g   | Prothrombin time/international normalized ratio                          |
| High-sensitivity C-reactive protein (hsCRP)                        | Exploratory storage samples (urine, serum, plasma, RNA, and whole blood) |
| Purified protein derivative (PPD) i                     | Pharmacogenetic sample (DNA)   |
| Urine pregnancy test d (assayed by clinical study site) | Immunogenicity testing (anti-ixekizumab Ab)                              |
| QuantiFERON®-TB Gold test i                             |  |
| T-SPOT® i   |  |
| HLA-B27  |  |

